## Appendix D Investigator Consent to Use of Personal Information

Takeda will collect and retain personal information of investigator, including his or her name, address, and other personally identifiable information. In addition, investigator's personal information may be transferred to other parties located in countries throughout the world (eg, the United Kingdom, United States, and Japan), including the following:

- Takeda, its affiliates, and licensing partners.
- Business partners assisting Takeda, its affiliates, and licensing partners.
- Regulatory agencies and other health authorities.
- IRBs and IECs.

Investigator's personal information may be retained, processed, and transferred by Takeda and these other parties for research purposes including the following:

- Assessment of the suitability of investigator for the study and/or other clinical studies.
- Management, monitoring, inspection, and audit of the study.
- Analysis, review, and verification of the study results.
- Safety reporting and pharmacovigilance relating to the study.
- Preparation and submission of regulatory filings, correspondence, and communications to regulatory agencies relating to the study.
- Preparation and submission of regulatory filings, correspondence, and communications to regulatory agencies relating to other medications used in other clinical studies that may contain the same chemical compound present in the study medication.
- Inspections and investigations by regulatory authorities relating to the study.
- Self-inspection and internal audit within Takeda, its affiliates, and licensing partners.
- Archiving and audit of study records.
- Posting investigator site contact information, study details and results on publicly accessible clinical trial registries, databases, and websites.

Investigator's personal information may be transferred to other countries that do not have data protection laws that offer the same level of protection as data protection laws in investigator's own country.

Investigator acknowledges and consents to the use of his or her personal information by Takeda and other parties for the purposes described above.

[figure not shown]
## **Appendix E** Sample of Subject Diary and The Bristol Stool Scale

This table provides a sample of the subject diary, which will be provided to subjects on Day -15 of the Screening Visit and in which they are to record every defecation event from Day -15 until Day 29. The diary prompts the subject to record all details of each event including the consistency of the stool and the difficulty they have in passing it. The second page of the appendix is the Bristol Stool Scale, which will be supplied to the subjects as an aid.

A. Date and time they take the study drug
B. After a bowel movement:
a. Date and time
b. Stool consistency
1 = Hard and round (difficult-to-pass) stool like those of rabbits
2 = Sausage-shaped but hard stool
3 = Sausage-shaped stool with cracks on the surface
4 = Sausage-shaped, soft stool with smooth surface, or coiled stool (like a snake)
5 = Soft, half-solid (and easy-to-pass) stool with clear crease
6 = Unshaped, loose stool with small, irregular-shaped pieces, or mushy stool
7 = Watery stool without solid pieces (entirely liquid)
c. Degree of straining:
0 = No straining
1 = Mild straining
2 = Moderate straining
3 = Strong straining
4 = Very strong straining
d.
Yes =
$N_0=$
C. Abdominal symptom (bloating and discomfort)
Abdominal bloating:
0 = None (no abdominal distention)
1 = Mild (Slight abdominal distention)
2 = Moderate (Abdominal distention clearly felt)
3 = Severe (Severe abdominal distension)
4 = Very severe (Extremely strong abdominal distension)
Abdominal discomfort:
0 = None (no abdominal discomfort)
1 = Mild (Slight abdominal discomfort)
2 = Moderate (Abdominal discomfort clearly felt)
3 = Severe (Abdominal discomfort with pain)
4 = Very severe (Abdominal discomfort with severe pain)
D. Date and time a rescue medication was used (if applicable)
E. Concomitant drugs (if applicable)

The investigator or clinical research coordinator will instruct the subjects to keep the diary throughout the study. If the investigator or coordinator asks a subject about diary entries and adds a note or corrects the diary for clarification, each note/correction will be marked with the date and signature and the reason for the correction. The investigator will maintain the diaries as part of the subject's file at the site.

# **Bristol Stool Chart**

Source: National Institute of Diabetes and Digestive and Kidney Diseases. [5]

A Phase 3, Multicenter, Randomized, Double-Blind, Parallel-Group, Placebo-Controlled Study to Evaluate the Efficacy and Safety of Lubiprostone for the Treatment of Chronic Idiopathic Constipation

#### CONFIDENTIAL INFORMATION

Do not distribute outside of Takeda without a confidentiality agreement.

CROSS-REGIONAL TEMPLATE			
Template Number:	C-TMPL-DO-801	Page:	5 of 31
Version Number:	1.2	Effective Date:	14 Sep 2015
This version replaces	s: 1.1		
Parent Document:	C-SOP-DO-800		
Template Title:	Statistical Analysis Plan (Legacy Takeda)		

	CROSS-REGIONAL TEMP	PLATE	
Template Number:	C-TMPL-DO-801	Page:	6 of 31
Version Number:	1.2	Effective Date:	14 Sep 2015
This version replaces:	1.1		
Parent Document:	C-SOP-DO-800		
Template Title: St	atistical Analysis Plan (Legacy Takeda	a)	
3.0 LIST OF ABBRE	EVIATIONS		
AE	adverse event		
ALT	alanine aminotransferase		
ANCOVA	analysis of covariance		
ANOVA	analysis of variance		
AST	aspartate aminotransferase		
BID	bis in die (twice a day)		
BM	bowel movement		
BMI	body mass index		
BUN	blood urea nitrogen		
CIC	chronic idiopathic constipation		
СРК	creatine phosphokinase		
CRF	case report form		
ECG	electrocardiogram		
FAS	full analysis set		
GGT	$\gamma$ -glutamyl transferase		
HIV	human immunodeficiency virus		
ICH	International Conference on Harmonisatio	n	
IVRS	Interactive Voice Response System	, ii	
LDH	lactate dehydrogenase		
LLN	lower limit of normal		
LOCF	last observation carried forward		
MedDRA	Medical Dictionary for Regulatory Activity	ties	
	milligram		
mg PAC-QoL	patient assessment of constipation – quality	ty of life	
PD	pharmacodynamics	ty of file	
PK	pharmacodynamics		
QOL	quality-of-life		
PPS	per protocol set		
PRO	patient-reported outcome		
SAE	serious adverse event		
SAF			
	safety analysis set		
SAP SPM	statistical analysis plan		
SBM	spontaneous bowel movement		
SD SDD	standard deviation		
SDB TL Co	standard database		
TLGs	tables, listings, and graphs		
ULN	upper limit of normal		
WHODrug	World Health Organization Drug Dictiona	ury	

Printed or downloaded documents must be verified against the effective version.

# 4.0 OBJECTIVES

#### 4.1. PRIMARY OBJECTIVES

The primary objective of this study is to evaluate the efficacy and safety of oral administration of lubiprostone 24  $\mu$ g BID for 4 weeks in subjects with CIC compared with placebo.

# 4.2. STUDY DESIGN

This is a phase 3, randomized, double-blind, parallel-group, placebo-controlled study in subjects with CIC as determined by the Rome III Diagnostic Criteria for Functional Constipation [4]. This study consists of a 14-day Screening Period, a subsequent 4-week (28 days) Double- Blind Treatment Period in which subjects will receive either lubiprostone or matching placebo BID and a 2 week follow-up period. Subjects will be randomized to either active lubiprostone or placebo in a 1:1 ratio. During the Screening Period, the defecation behavior of each subject is recorded in a diary to confirm he/she has constipation. The subject diary will be distributed on Study Days - 15, -1, 8 and 15. Subjects will be instructed to keep the diary every day including on the morning of Visit 1 for the entire week.

Use of all existing laxatives is stopped at the beginning of the Screening Period (Visit 1). Subjects are instructed not to change their diet or lifestyle habits during the study. A total of 10 mg of bisacodyl suppository (or any equivalent drug) may be prescribed as a standard rescue medication if a subject has no adequate bowel movement for 3 consecutive days during the Screening Period of the study. When bisacodyl suppository does not improve constipation, glycerin enema (or equivalent drug) will be given. Subjects are instructed to complete their diaries before using rescue medications.

If the rescue medications fail to improve constipation, the investigator may decide to use another rescue medication. The recommendation may include a medication from the excluded medication list other than any form of polyethylene glycol, linaclotide, methylnaltrexone, or prucalopride, all of which are considered prohibited rescue medications. No rescue medication may be given 24 hours prior to and until 48 hours after the first dose of the study drug (Day 1). Subjects who use a rescue medication within 24 hours before the first dose of study drug on Day 1 should be withdrawn from the study. Those who use a rescue medication within 48 hours after dosing on Day 1 will be discontinued from the study by the investigator. The dose and mode of administration of rescue medications must be recorded in the electronic case report form (eCRF).

Approximately 150 subjects whose constipation is confirmed during the Screening Period will be randomized in the Double-Blind Treatment Period to receive either lubiprostone or matching placebo BID. Others whose constipation does not satisfy the criteria during the 14-day Screening Period or those who receive a rescue medication within 24 hours prior to the first dose on Day 1 are ineligible for randomization in the Double-Blind Treatment Period and therefore will be excluded from the study. Subjects who satisfy the inclusion criteria and do not meet the

CROSS-REGIONAL TEMPLATE			
Template Number:	C-TMPL-DO-801	Page:	9 of 31
Version Number:	1.2	Effective Date:	14 Sep 2015
This version replaces:	1.1		
Parent Document:	C-SOP-DO-800		
Template Title: St	tatistical Analysis Plan (Legacy Takeda)		

exclusion criteria are randomized to 1 of the treatment groups in the order of the number assigned. Approximately 150 subjects with CIC will be randomized to 2 groups: active treatment or placebo in a 1:1 ratio (75 subjects each) in a double-blinded manner.

Subjects will be instructed to take 1 capsule BID, orally, at the same time of the day, preferably in the morning with breakfast and in the evening with dinner. Subjects are to begin their study drug treatment in the morning with breakfast following Visit 2.

Subjects will return to the study site on approximately Study Days 8, 15, and 29 during the 4 weeks of double-blind treatment and will be followed for an additional 2 weeks during the Follow-Up Period, in which no treatment will be administered.

At the investigator's discretion, with consideration to subject's bowel movement frequency and consistency, dose adjustments (dose reduction) may be made in a double-blind manner. Dose adjustment should be documented in the subject's source notes. Procedure for reduction of study drug dose due to Adverse Events is described in Section 7.7.

Subjects who withdraw prematurely will be seen within 1 week of discontinuation for an Early Termination Visit. A schematic of the study design is included as Figure 1. A schedule of assessments is listed in Appendix A.

#### **Figure 1 Schematic of Study Design**

Printed or downloaded documents must be verified against the effective version.

**CONFIDENTIAL INFORMATION** Do not distribute outside of Takeda without a confidentiality agreement.

CROSS-REGIONAL TEMPLATE				
Template Number:	C-TMPL-DO-801	Page:	10 of 31	
Version Number:	1.2	Effective Date:	14 Sep 2015	
This version replaces	s: 1.1			
Parent Document:	C-SOP-DO-800			
Template Title:	Statistical Analysis Plan (Legacy Takeda)			

ATE

ODOOD DEOLONIAL TEMPL

# 5.0 ANALYSIS ENDPOINTS

#### **Primary Endpoint**

Spontaneous bowel movement (SBM) frequency in Week 1 of study drug administration.

#### **Secondary Endpoints**

SBM frequency (Week 2, 3, and 4).

Proportion of subjects who have a SBM within 24 hours after first dose.

Mean degree of straining (Week 1, 2, 3, and 4).

Mean degree of stool consistency (Week 1, 2, 3, and 4).

Weekly abdominal symptoms score (bloating and discomfort) (Week 1, 2, 3, and 4).

Weekly responder rate (Week 1, 2, 3 and 4)

#### **Additional Endpoints**

Quality of life evaluation using the standard Patient Assessment of Constipation-Quality of

Life (PAC-QOL) Questionnaire.

## Safety

The safety of lubiprostone will be evaluated by the following parameters:

Adverse events (AEs)

Clinical laboratory values.

Vital signs, including body temperature, blood pressure, heart rate, and body weight.

Physical examination.

## **Exploratory Endpoints**

	CROSS-REGIONAL TEMPI	_ATE	
Template Number:	C-TMPL-DO-801	Page:	11 of 31
Version Number:	1.2	Effective Date:	14 Sep 2015
This version replaces:	1.1		
Parent Document:	C-SOP-DO-800		
Template Title:	Statistical Analysis Plan (Legacy Takeda)		

# 6.0 DETERMINATION OF SAMPLE SIZE

Assuming equal allocation, a power of 90%, an alpha level of 0.05 for a 2-sided test, a placebo mean of 4 (standard deviation of 2.7), and a treatment mean of 5.9 (standard deviation of 4) for SBM frequency at Week 1 and using the Wilcoxon-Mann-Whitney test [1], a total sample size of 146 is required. The Wilcoxon-Mann-Whitney test is a non-parametric test of the null hypothesis that the distribution is the same for both placebo and treatment responses against the alternative that there is a location difference between the two. The primary analysis will be conducted using the van Elteren test, which is a stratified version of the Wilcoxon-Mann-Whitney test, use of the Wilcoxon-Mann-Whitney test for sample size estimation will provide an approximate sample size for the van Elteren analysis. The estimates of placebo and treatment response are based on a previous study conducted by Sucampo Pharmaceuticals in the United States of America (Protocol No. RTU/0211SC0131).

The primary endpoint requires subjects to complete at least 4 days of the study diary, therefore assuming a non-evaluable rate of 3% by Day 4 an additional 4 subjects are required, giving a total of 150 subjects.

1 5

	CROSS-REGIONAL TEMP	LATE	
Template Number:	C-TMPL-DO-801	Page:	12 of 31
Version Number:	1.2	Effective Date:	14 Sep 201
This version replaces	s: 1.1		
Parent Document:	C-SOP-DO-800		
Template Title:	Statistical Analysis Plan (Legacy Takeda)	)	

# 7.0 METHODS OF ANALYSIS AND PRESENTATION

# 7.1 GENERAL PRINCIPLES [OR CONSIDERATIONS]

Continuous data will be summarized using number of subjects (N), mean, standard deviation (SD), median, minimum, and maximum. Summary statistics for continuous data will only include subjects with a non-missing value for the data being summarized.

Categorical data will be summarized using the number and percent of subjects for each category where appropriate. Missing categories will be used for categorical data when missing data is present. The calculation of percentages will take into account missing responses.

All confidence intervals, statistical tests, and resulting p-values will be reported as 2-sided unless otherwise stated. P-values (when rounded to three decimals) less than or equal to  $\alpha$  (=0.05) are reported as "statistically significant".

Means, LS means, and medians will be presented to 1 more decimal place than the recorded data. Where presented, SDs and standard errors will be presented to 2 more decimal places than the recorded data. Confidence intervals for parameter estimates will be presented using the same number of decimal places as those recorded for the parameter point estimate.

Alternative methods of analysis of the data may be considered prior to un-blinding should some of the assumptions underlying the proposed analyses not be met. However, the reasons for any departures from the planned approach and methods will be documented fully.

Centers may be pooled geographically if necessary for analysis purposes.

Version 9.4 or later of SAS®, will be used to provide all data summaries, statistical analyses, and data listings.

CROSS-REGIONAL TEMPLATE				
Template Number:	C-TMPL-DO-801	Page:	13 of 31	
Version Number:	1.2	Effective Date:	14 Sep 2015	
This version replaces:	1.1			
Parent Document:	C-SOP-DO-800			
Template Title: S	Statistical Analysis Plan (Legacy Takeda)			

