# 7.8 EFFICACY ANALYSIS

The primary and secondary endpoints will be derived from the daily diary data entered by patients.

Two-sided tests at a significance level of  $\alpha$ =5% will be used throughout unless otherwise stated. The null hypothesis is that lubiprostone is equal to placebo against the alternative that lubiprostone is different to placebo. All analyses will be performed using the FAS. Analyses specified for the PP are to be regarded as supportive evidence. There will be no adjustment for multiplicity.

All efficacy endpoints will be summarized by treatment and visit. If baseline measures are also defined and collected for an efficacy endpoint then change from Baseline at each visit will also be presented by summary statistics by treatment and visit. Change from baseline will be calculated as (post-baseline value) – (baseline value). Baseline is defined as the last recorded measurement prior to treatment.

For diary data, baseline values will be the average of all diary data from the screening period (Days -14 through -1, inclusive, relative to day of first dose). If more than 14 days of diary data are collected during the screening period only the data from Day -14 onwards will be used. If fewer than 8 days are available then the baseline value will be set to missing.

Centers may be pooled geographically if necessary for analysis purposes. This will be determined before database lock.

CROSS-REGIONAL TEMPLATE				
Template Number:	C-TMPL-DO-801	Page:	20 of 31	
Version Number:	1.2	Effective Date:	14 Sep 2015	
This version replaces:	1.1			
Parent Document:	C-SOP-DO-800			
Template Title: S	statistical Analysis Plan (Legacy Takeda)			

For weekly SBM frequency, at least 4 days of diary data are required to compute a weekly estimate, if there are less than 4 days recorded in a week then the SBM frequency for that week will be set to missing.

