## Primary Analysis

Since outliers are commonly observed in these data, parametric models may not be robust. The efficacy data will therefore be analyzed by a van Elteren test stratified by center. If necessary, small centers will be pooled as mentioned above. This procedure will test the null hypothesis of equal SBM rates between treatments at the end of Week 1 versus the alternative hypothesis of non-equality between the 2 groups; the test will be conducted at a 2-sided significance level of 0.05. A related 95% confidence interval and point estimate will be provided for the treatment difference; the confidence interval will be estimated by inverting the hypothesis test. This endpoint will be analyzed for the FAS.

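### SAP 7.1 compares the p-value with 0.05 after rounding it to three decimals, so the nominal cut-off is just below 0.0505 instead of the stated two-sided 0.05

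*SAP*

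**What the plan says.** SAP 7.1 states: "All confidence intervals, statistical tests, and resulting p-values will be reported as 2-sided unless otherwise stated". It then sets the rule for the label: "P-values (when rounded to three decimals) less than or equal to" alpha, given there as 0.05, are reported as statistically significant. This is the only sentence in the SAP that says when a result earns that label.

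The level itself is set in other places, none of which mentions rounding:

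- SAP 7.8 and Protocol 13.1.3 both specify "Two-sided tests at a significance level of" 5%.
- SAP 7.8.1, Primary Analysis, says of the van Elteren test that "the test will be conducted at a 2-sided significance level of 0.05". For the accompanying 95% interval it says that "the confidence interval will be estimated by inverting the hypothesis test".
- SAP 6.0 plans the sample size with "an alpha level of 0.05 for a 2-sided test", and Protocol 13.3 uses the same level.

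SAP 7.13 describes the SAP as adding detail and further analyses to the protocol. It does not declare a change to the significance rule.

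**The concern.** Rounding a p-value for a table is harmless. Applying the threshold to the rounded value is not quite the same thing, because it moves the threshold. Under SAP 7.1 as written, every p above 0.0500 and below 0.0505 is displayed as 0.050 and labelled significant, although it exceeds the level that the protocol and the rest of the SAP set.

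The study is meant to support registration. If the primary p-value fell in this band, the two rules would give opposite answers, and the choice between them would be made after the result was known. The report could then show a result labelled significant beside a 95% confidence interval, obtained by inverting the same test, that generally includes no difference. The rule also covers every other p-value in the report, with no multiplicity adjustment.

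**Working it through.** **The plan's own figure.** The sample size was reproduced first, to confirm the level on which the design rests. The inputs from SAP 6.0 are means of 4 and 5.9, SDs of 2.7 and 4, 90% power, two-sided alpha 0.05 and equal allocation.

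- Root-mean-square SD = √((2.7² + 4²)/2) = √11.645 = 3.412; difference = 5.9 − 4 = 1.9.
- A two-sample t-test (noncentral t) needs 69 per arm.
- Dividing by the Wilcoxon asymptotic relative efficiency, 3/π = 0.9549, gives 69/0.9549 = 72.3, so 73 per arm and 146 in total.

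This matches the stated 146, so the design was sized at 0.05.

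**The cut-off implied by SAP 7.1.** Round first, then compare with 0.05:

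| Unrounded p | Rounded (half up) | Label under SAP 7.1 | Unrounded p ≤ 0.05? |
|---|---|---|---|
| 0.0500 | 0.050 | significant | yes |
| 0.05001 | 0.050 | significant | no |
| 0.0504 | 0.050 | significant | no |
| 0.0504999 | 0.050 | significant | no |
| 0.0505 | 0.051 | not significant | no |

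The SAP does not state a rounding convention. Under half-to-even, exactly 0.0505 would also pass, which makes no practical difference.

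**Size of the band.** The excess is 0.0505 − 0.0500 = 0.0005, and 0.0005/0.05 = 1%. On the z scale, z(0.0505/2) = 1.9557 and z(0.05/2) = 1.9600.

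**Chance of falling in it, for one test.**

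- Under the null with a continuous p-value: 0.0005.
- At the planned power: noncentrality = 1.9600 + 1.2816 = 3.2415 (from unrounded terms). Power is Φ(3.2415 − 1.9600) = 0.9000 at 0.05 and Φ(3.2415 − 1.9557) = 0.9007 at 0.0505. The difference from unrounded values is 0.00075, or 1 in about 1,340.
- With 73 per arm and the efficiency-adjusted t-test, power moves from 0.9039 to 0.9046. Sample size does not change.

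**All main comparisons.** The secondary endpoints in SAP 5.0 give 3 (SBM frequency) + 1 (SBM within 24 hours) + 4 (straining) + 4 (consistency) + 8 (two abdominal symptoms over four weeks) + 4 (responder rate) = 24, or 25 with the primary. If all were null, the expected number in the band would be about 25 × 0.0005 = 0.0125.

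**Realised size of the test.** Weekly SBM frequencies are mostly whole numbers with ties, so the van Elteren test was simulated under the null. It used stratum weights 1/(n+1), a tie-corrected variance and the normal approximation, with 400,000 trials of 150 subjects per layout. The counts were negative binomial with mean 4 and SD 2.7, the placebo values in SAP 6.0. The negative binomial form and the center layouts are assumptions; the protocol summary says only that there are about 10 sites.

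| Center layout | Rejection, unrounded p ≤ 0.05 | Rejection, SAP 7.1 rule |
|---|---|---|
| 10 centers of 15 | 0.0493 | 0.0498 |
| 5 centers of 30 | 0.0503 | 0.0508 |
| 10 uneven centers (34 down to 4) | 0.0503 | 0.0508 |
| One stratum | 0.0503 | 0.0508 |

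The Monte Carlo standard error of each rate is √(0.05 × 0.95/400,000) ≈ 0.00035. The increment from rounding, counted within the same trials, is 0.00048 to 0.00053.

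**The case against.** The strongest reply is that SAP 7.1 is a reporting convention. It sits in the section on methods and presentation, decimal-place rules follow it directly, and it speaks of what is reported. SAP 7.8.1 separately fixes the level of the primary test at 0.05. If the specific text governs the general, the test is already at 0.05 and only a label in a table could differ. No stated figure is miscalculated, and the rule is pre-specified and treats both arms alike.

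The effect is also tiny. At unrounded p ≤ 0.05, simulated rejection across the assumed layouts runs from 0.0493 to 0.0503. That spread of 0.0010 is twice the rounding effect, although part of it may be simulation noise. With ties, agreement between the interval and the test is not guaranteed even without rounding.

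The remarks on size stand, and they are why the point is minor. The conflict with the interval is likewise only partly due to this sentence. The reporting-convention reading does not dispose of the point. The sentence applies the threshold to the rounded number, and SAP 7.8.1 gives a level without saying how the p-value is compared with it. Neither document states which section takes precedence, so a programmer following the SAP literally would label p = 0.0504 significant.

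**Conclusion.** The concern holds, at minor severity and with high confidence. The decision threshold in SAP 7.1 does not match the two-sided 0.05 stated in SAP 6.0, 7.8 and 7.8.1 and in Protocol 13.1.3 and 13.3. The figure of 0.0505 is a nominal cut-off: it does not mean that the trial's realised type I error is materially inflated, and the simulation puts that error near 5%. The discrepancy has a consequence only if an unrounded p-value lies above 0.0500 and below 0.0505.

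The cut-off follows from the SAP's wording and assumes conventional rounding to three decimals. The probabilities assume a continuous p-value and, for the power figure, a normal approximation at exactly 90% power. The simulated rates depend on the assumed count distribution and center layouts, but the increment was essentially the same in all four.

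**What to change.** Replace the labelling sentence in SAP 7.1 with: *Statistical significance is judged on the unrounded p-value (p ≤ 0.05); rounding to three decimals is for display only.*

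Protocol 13.1 requires the SAP to be final before unblinding, so the change should be made by then. It costs one sentence, with no operational burden and no effect on sample size. A p-value that falls in the band would still print as 0.050, so in that case the report should show a fourth decimal to make the conclusion legible.
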